9. STATISTICAL ANALYSIS

The endpoints with respect to percentages at day 7, day 28 (including the primary endpoint) and at 12 weeks will be analyzed using hierarchical models where intervention effects, (random) cluster effects, and random cluster-period effects will be analyzed. Time to events (for example response or death) will be analyzed using Kaplan Maier curves with log rank tests and Cox regression models.

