Rationale: Patients with haematological malignancies and chemotherapy induced prolonged neutropenia are at risk for severe bacterial and fungal infections. These opportunistic infections can result in prolonged hospital stay, increases costs and greater mortality. Voriconazole has now been recommended as the first line agent for invasive pulmonary aspergillosis (IA). Retrospective observational studies of voriconazole serum concentration suggest that serum concentration correlate with toxicity and clinical response. These observations were however made in small series of patients and data were collected retrospectively. These inherent methodological flaws make it impossible to draw definite conclusions about the effect of voriconazole serum concentration monitoring on the outcome of IA, and therefore considered insufficient proof to recommend voriconazole concentration determination in blood as standard of care. The impact that so-called serum concentration guided dosing of voriconazole will have on treatment success can only be evaluated through a prospective randomized clinical trial.

Objective: The objective of this study proposal is to determine whether pharmacologic optimization of voriconazole by means of therapeutic drug monitoring (TDM) results in improved patient outcomes (efficacy and safety) and is more cost-effective compared to the current standard of care.

Study design: we designed a prospective stratified cluster randomized cross-over trial of therapeutic drug monitoring in patients with haematological disease who have developed IA. The order of periods (TDM or standard of care, each 12 months) will be randomized per centre.

Study population: Patients with haematological malignancies and possible, probable or proven IA according to EORTC criteria.

Intervention (if applicable): In the intervention group the voriconazole dosage will be adjusted to achieve trough blood concentrations in a predefined window of 2-5 mg/L. In the control group voriconazole will be dosed according to product leaflet.

Main study parameters/endpoints: The primary clinical endpoint will be a global response consisting of a combined endpoint of toxicity and response to therapy (clinical, microbiologic and radiologic responses) 28 days after starting treatment with voriconazole. A sample size of n=192 is needed to detect a 20% absolute reduction in the number of

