3. STUDY DESIGN

As the number of patients treated for invasive aspergillosis in each hospital is limited, a multi centre set up is required to have a study powered to detect a clinically relevant difference in outcome between the intervention group and the control group. For this study a cluster randomized design - instead of a randomisation at patient level - was chosen to minimize logistic problems, optimize inclusion of patients and limit bias during the study. Blinding the intervention would increase the costs of the study considerably without providing better results. The cross-over design was chosen to diminish influences by centre, as the inter-centre variability in facility and treatment can influence outcome of treatment. Differences which are found can now be attributed solely to the intervention as the centre serves as its own control. As this study will be performed in several centres with random start with standard care or with TDM-tailored treatment, we anticipate that the time-based biases will be negligible. To diminish the carry-over effect from one period to the next a wash-out period of 28 days is established, which equals the time of start of treatment until evaluation on the primary endpoint. This prevents that two treatment protocols, intervention and control are operational at the same time. For these reasons we choose a cluster randomized cross-over design in which every cluster receives both interventions during two consecutive periods (TDM and standard care, 12 months each). This longitudinal design was previously successfully used in the Netherlands [32]. Randomization by a computer-generated randomization system determines the sequence within in each cluster. In this way the variability between clusters is taken into account, this results in an improved power. The randomization will be stratified to obtain equally balanced clusters with respect to experience and size. At six months, inclusion will be evaluated and it will be estimated whether duration per period has to be increased or decreased and whether the clusters are still balanced. The intervention (TDM) consists of taking serum samples at day three of treatment, measuring the voriconazole serum levels and adjusting the dosage to reach the therapeutic window. Dosing of voriconazole will be done during the control period according to the product brochure.

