4. STUDY POPULATION

4.1 Population (base)

There is a considerable variability in host-specific factors in the targeted population of this study resulting in a heterogeneous population. Reducing the heterogeneity of the population or stratification for all key variables [28] will result in an inadequately powered study due to a lack of sufficient numbers of eligible subjects. However, due to participation of 13 centre's we are able to reduce variability in patients by narrowing the inclusion criteria, (i.e. exclusion of the group *other patients* (non-hematological malignancies and solid organ transplant recipient)) compared to the study conducted by Herbrecht et al [16]. In previously conducted randomized controlled trials, stratification was performed for risk of infection and antifungal prophylaxis [17]. As diagnosing invasive fungal disease is difficult, the EORTC/MSG, defined three levels of probability of invasive fungal disease: possible, probable or proven invasive fungal disease. These definitions will be used in this study at baseline and again at the end of treatment.

In the Netherlands each year 100 patients are classified as possible, 70 patients as probable and 30 as proven IA. Most of these patients are treated in University Medical Centres, but larger peripheral centres also treat these patients. Due to competing studies from the pharmaceutical industry a part of these potentially eligible subjects will not be included. Due to the more strict in- and exclusion criteria, and refusal to consent, the number of subjects included in these studies will be relatively small. However, some of the eligible study participants will not participate as they refuse informed consent. If these two combined count for half of the patients that are potentially eligible to participate in this study, the number of study participants left to participate in this trial will be sufficient, as by virtue of the trial design of this study proposal, very few patients are expected to drop out.

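### The primary model as listed has no fixed period effect, so a change between the two years common to all centres would cost power and, with unequal sequences, add a small bias

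*Protocol*

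**What the plan says.** Section 9 of the protocol names the terms of the model for the percentage endpoints at day 7, day 28 (the primary) and 12 weeks. They "will be analyzed using hierarchical models where intervention effects, (random) cluster effects, and random cluster-period effects will be analyzed". The same sentence appears in the table of contents. Neither place lists a period effect common to all centres.

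Section 3 describes the design: "every cluster receives both interventions during two consecutive periods (TDM and standard care, 12 months each"). The Summary adds: "The order of periods (TDM or standard of care, each 12 months) will be randomized per centre". Section 3 also says of the allocation: "The randomization will be stratified to obtain equally balanced clusters with respect to experience and size".

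On calendar time, section 3 says "we anticipate that the time-based biases will be negligible", and section 10.2 repeats the statement. Section 3 also claims: "Differences which are found can now be attributed solely to the intervention as the centre serves as its own control".

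On the number of centres, section 4.4 bases the sample size on at least 12, while section 4.1 argues from more eligible patients "due to participation of 13 centre's". A review of inclusion after six months is planned, at which "it will be estimated whether duration per period has to be increased or decreased and whether the clusters are still balanced".

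**The concern.** Within a centre, the comparison of TDM with standard care is a comparison of one year with the other. Suppose failure risk changes everywhere between those years, for example through diagnostics or supportive care. The centre's TDM-minus-control difference then moves one way in centres that start with TDM and the other way in centres that start with standard care.

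A random cluster-period effect does not capture this. It represents independent noise for each centre-year, whereas the change is a single shift shared by all centres. Without a fixed term, the shift is counted as extra cluster-period variance, and the standard error of the intervention effect grows.

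Two things are at stake. The first is power, which is planned at only about 80%, with 8 patients in reserve (200 against 192). The second is a bias, if one sequence carries more patients than the other, because the shift then no longer cancels.

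**Working it through.** **Inputs from the protocol (section 4.4).** Failure 40% versus 20%; two-sided 5%; 12 centres of 16 patients, so 8 per centre-period; correlation 0.002 to 0.02; 192 patients; power about 80%. Section 4.1 gives 13 centres.

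**Assumptions, not in the documents.** The size of the change between periods (δ), and a between-period correlation of 0.

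**1. The plan's own figure.** The usual two-proportion formula needs 82 patients per arm. With a correlation of 0.02 within a centre-period and 0 between periods, the design effect is 1 + (8 − 1) × 0.02 = 1.14. Then 2 × 82 × 1.14 ≈ 187, or 188 as an even total. With 96 per arm, power is 81.4%. The stated 192 is therefore reproduced closely. That formula uses a normal reference and no change over time.

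**2. Power with and without the period term.** Use the TDM-minus-control difference of each centre. Its variance is

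(0.4 × 0.6 + 0.2 × 0.8) / 8 × 1.14 = 0.40 / 8 × 1.14 = 0.057.

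If period is omitted and the sequences are equal, the differences scatter by a further ±δ, so the variance used by the test is about 0.057 + δ². The noncentrality is 0.20 / √(variance / 12). The t reference has 11 degrees of freedom without the term (critical value 2.201) and 10 with it (2.228).

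| Change δ | Variance, no term | Noncentrality | Power, no term | Power, with term |
|---|---|---|---|---|
| 0 | 0.0570 | 2.90 | 75.2% | 74.4% |
| 3 points | 0.0579 | 2.88 | 74.6% | 74.4% |
| 5 points | 0.0595 | 2.84 | 73.5% | 74.4% |
| 10 points | 0.0670 | 2.68 | 68.4% | 74.4% |
| 15 points | 0.0795 | 2.46 | 61.0% | 74.4% |

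The last column is held constant because the term removes δ from the residual. This ignores the small effect of δ on the binomial variances. The level is below the 81.4% of step 1 mainly because of the t reference with few centres.

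**3. Check by simulation.** The stated model was approximated by a linear mixed model on centre-period proportions, with 2,000 runs per cell (Monte Carlo error about 1 point). Assumed logit-scale standard deviations were 0.25 for centre and 0.20 for centre-period. Power without → with the term:

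| Sequences | No change | About 10 points | About 20 points |
|---|---|---|---|
| 6:6 | 0.81 → 0.81 | 0.75 → 0.79 | 0.61 → 0.77 |
| 7:6 | 0.82 → 0.82 | 0.78 → 0.83 | 0.59 → 0.81 |
| 8:5 | 0.83 → 0.81 | 0.70 → 0.79 | 0.42 → 0.80 |

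Under no intervention effect and 6:6, the rejection rate without the term is about 0.03 at a 10-point change and 0.01 to 0.02 at 20 points. The test is conservative there.

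**4. Bias.** Let s be the share of patients in one sequence. The pooled difference is shifted by δ × (2s − 1). For equal-sized centres:

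- 6:6: 2 × 6/12 − 1 = 0, no bias.
- 7:6: 2 × 7/13 − 1 = 1/13, so 0.77 points per 10-point change.
- 8:5: 2 × 8/13 − 1 = 3/13, so 2.3 points per 10-point change.

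The simulations agree: under no effect and a 10-point change, the mean estimate is off by about 0.6 to 0.8 points at 7:6 and 2.4 at 8:5. It is about 0 with the term.

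**The case against.** The strongest reply is that the omission may cost nothing. No figure in the protocol points to a change between the two years. For a change of 3 points the two models have equal power to within 0.2 points, and at 5 points the loss is under 1 point. The larger losses need changes of 10 points or more, which is a lot against a 40% failure rate in consecutive years. All of this stands, and it limits the weight of the point.

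A reader might also infer that arm is confounded with calendar time. The documents do not support that. The order is randomised per centre, so both arms run in both years, and arm is close to orthogonal to period across the trial. The tie exists only within a centre.

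A reader might infer that the primary estimate is bound to be biased because 13 centres cannot split evenly. Bias also needs a change over time. At 7:6 it is under 1 point per 10-point change, against a target of 20 points. The stratification by size and experience limits imbalance in patient numbers, and section 4.4 works with 12 centres. Nor does the omission threaten false positives with balanced sequences, because it makes the test conservative.

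Finally, it may be said that section 9 is an outline whose detail belongs in a statistical analysis plan. That is fair for patient-level covariates. It is weaker for the period term, because section 9 does list the model's effects, and section 3 sets time effects aside on expectation alone.

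**Conclusion.** The point holds in a limited form. The listed model leaves out a fixed period effect that a two-period cross-over by centre calls for, and the random cluster-period term does not replace it.

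The main consequence is loss of power, conditional on a common change of unknown size. On the analytic calculation the loss is under 1 point up to a 5-point change, about 6 points at 10 (74.4 − 68.4) and about 13 at 15 (74.4 − 61.0). The mixed-model simulation gives a milder 3 to 5 points at a 10-point change for 6:6 or 7:6. These figures rest on the correlation of 0.02 within and 0 between periods, or on the assumed variance components of the simulation. The simulation also uses a linear model in place of a logistic one.

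Bias is secondary: none with balanced sequences and sizes, and small with a 7:6 split.

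One further reading should be resisted. Different patients enter in each period, so a reader might fault the model for having no baseline case-mix terms. The choice of such covariates is commonly left to the statistical analysis plan, which was not available here. Chance differences in case mix between centre-periods are already covered by the random cluster-period effect. The protocol also does not clearly provide a separate panel-assigned baseline EORTC/MSG category to adjust for. Case-mix adjustment is therefore not part of this finding.

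**What to change.** In section 9, add period (first or second) as a fixed effect to the hierarchical model for all percentage endpoints, alongside the intervention, random cluster and random cluster-period effects already listed.

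This changes analysis wording only. It uses one degree of freedom. If there is no change over time, power falls from 75.2% to 74.4% in the calculation above, and it needs no extra patients or data. In return, the result no longer depends on the expectation that time effects are negligible.

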1. INTRODUCTION AND RATIONALE

Patients with prolonged and severe neutropenia (neutrophils $<0.5 \times 10^9/L$ for >10 days), are at risk for life-threatening infections especially invasive pulmonary aspergillosis. The risk of invasive Aspergillosis (IA) increases with the severity and duration of neutropenia. Patients treated for haematologic malignancies with intensive chemotherapy and hematopoietic stem cell transplant recipients are at particularly high risk [6-10]. Other risk factors for IA include Graft-Versus-Host Disease and its treatment with corticosteroids, previous invasive mould infection and high environmental exposure to fungal spores in ambient air [11-14]. As the reported response to antifungal therapy is low (50%) and mortality high (30-50%) there is still an urgent need to improve treatment [23-25].

Every year, about 200 patients in the Netherlands with haematological malignancies, are treated with voriconazole for invasive fungal infection. This translates into 15-25 patients per centre annually. When patients encounter an invasive fungal infection the chemotherapy for the haematological malignancy is often interrupted or sometimes continued in a reduced intensity. This results in a suboptimal treatment of the underlying malignancy. The results of antifungal therapy are far from optimal with response rates for voriconazole and lipid amphotericin B being approximately 50%. The overall mortality at 12 weeks is still 30-50%. Clearly, there is a dire need to improve treatment outcome for IA. Haematologists, in consultation with an infectious diseases specialists, medical microbiologists and hospital pharmacists put effort in optimizing treatment in this critically ill patient population.

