4.4 Sample size calculation

In a previous randomized trial with voriconazole in a dosage according to product leaflet with similar inclusion criteria the response was: complete in 20%, partial in 30%, stable in 10% and failure in 40% [16]. As TDM will probably result in the largest benefit in patient with low voriconazole trough levels, who are not responding, or in patients with high trough levels, who stopped because of side effects, the sample size calculation of this study is based on the reduction of patients failing on voriconazole therapy. For control patients (treated without TDM) a failure rate of 40% is expected [16], while for patients during the experimental TDM episode, a failure of 20% is expected. Under the most unfavourable assumption that the intra cluster correlation coefficient equals the intra period correlation coefficient varying between 0.002 and 0.02, and knowing that at least 12 centres are participating in this study, each cluster must include 16 patients to obtain a power of about 80% with an unreliability of 5% (two-sided) to detect a clinically relevant improvement of 20% of reduction of patients failing on voriconazole at day 28 of treatment compared to control. This means that in total 192 patients are necessary for performing this study. To compensate for loss during follow-up in total 200 patients will be included. Loss during follow-up is defined as patients not willing to continue participation because of personal reasons. Patient stopping because of voriconazole adverse effects are noted as "failure".

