7.1.2 Secondary study parameters/endpoints (if applicable)

- 1) mortality at day 28 and week 12 of therapy due to fungal infection, overall mortality at 28 days and 12 weeks.
- 2) resolution of neutropenic fever, defined as percentage of patients with a oral temperature of $<38\text{ }^{\circ}\text{C}$ at day 7 of voriconazole treatment [17]; time (in days) to resolve fever is also noted.
- 3) percentage of voriconazole serum concentrations within the targeted window of 2-5mg/L during therapy based on repeated measurements in time.
- 4) percentage switched to salvage therapy (i.e. amphotericin B or one of its lipid or liposomal formulations; or echinocandin (e.g., caspofungin/anidulafungin) or other triazole (e.g., posaconazole); or measured concentration level in control arm during treatment for toxicity or failure)

- 5) side effects (visual disturbance and liver enzymes) Side effects leading to drug discontinuation.
- 6) time (in days) of to global response as defined under the primary endpoint definition after the start of voriconazole
- 7) The evaluation of cost-effectiveness (hospital and societal per perspective) of voriconazole TDM in patients with invasive aspergillosis will be an integral part of this project.

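### The times to event are given log-rank and Cox analyses without the cluster cross-over structure, and the handling of death before response is left open (secondary endpoints only)

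*Protocol*

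**What the plan says.** Section 3 of the protocol states the design: "we choose a cluster randomized cross-over design in which every cluster receives both interventions during two consecutive periods". Section 4.4 sizes the trial on non-zero correlation, assuming that "the intra cluster correlation coefficient equals the intra period correlation coefficient varying between 0.002 and 0.02".

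Section 9 has two sentences on method. The first covers percentages at day 7, day 28 (the primary endpoint included) and 12 weeks, and prescribes "hierarchical models where intervention effects, (random) cluster effects, and random cluster-period effects will be analyzed". The second covers everything measured as a time: "Time to events (for example response or death) will be analyzed using Kaplan Maier curves with log rank tests and Cox regression models".

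The times concerned are secondary. Section 7.1.2 lists, as item 6, "time (in days) of to global response as defined under the primary endpoint definition", and under item 2 the days until fever resolves. Time to death appears only as an example in section 9. Section 7.1.1 categorises global response on day 28 and counts death as failure. Section 1 notes, as a percentage: "The overall mortality at 12 weeks is still 30-50".

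**The concern.** A standard log-rank test treats patients as independent and individually allocated. Here the treatment changes by centre and period, so patients in the same cluster-period share both the arm and local influences. Correlation within a cluster-period makes the unadjusted standard error too small. Centre differences that persist across both periods make it too large, because each centre serves as its own control and an unstratified test ignores that. The protocol accounts for both effects in one sentence of section 9 and names neither in the next.

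A patient who dies before responding can no longer respond. If such deaths are censored, one minus Kaplan-Meier estimates the response in a hypothetical setting without deaths and exceeds the share who actually respond. The excess would differ by arm if mortality did.

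Third, global response is categorised on day 28, and the only HRCT that section 7.3 ties to a time is the one at the start of treatment (plus or minus 3 days). A response date in days is therefore known only to lie between assessments.

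**Working it through.** **Inputs from the protocol.** Section 4.4: 12 centres, 16 patients per centre, correlation 0.002 to 0.02, failure 40% against 20%, two-sided 5%, power about 80%, total 192. Section 1: response about 50%.

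**Assumptions.** 16 per centre means m = 8 per cluster-period. The correlation of the day-28 binary outcome carries over to event times. Cause-specific hazards are constant. The documents do not give the share dying before response, so 10% to 40% is a range chosen here.

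**The plan's own figure.** Two proportions, 40% and 20%, pooled variance: [1.96 × √(2 × 0.3 × 0.7) + 0.8416 × √(0.24 + 0.16)]² / 0.2² = 81.2, so 82 per arm. The cluster cross-over design effect is

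DE = 1 + (m − 1)ρ_within − m ρ_between,

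where ρ_within is the correlation inside a cluster-period and ρ_between the correlation across the two periods of a centre. With ρ_within = 0.02 and ρ_between = 0, DE = 1 + 7 × 0.02 = 1.14 and N = 164 × 1.14 = 187. Power at 192 is then 81.4%. With a continuity correction (91 per arm) and ρ_between = 0.01, N = 182 × 1.06 = 193. The stated 192 is reproduced, so the same formula and correlations can be used to size the present point.

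**Effect of leaving clustering out.** The correct standard error is √DE times the unadjusted one. The true size of a nominal 5% test is 2 × P(Z > 1.96/√DE).

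| ρ_within | ρ_between | DE | √DE | True size | Simulated log-rank |
|---|---|---|---|---|---|
| 0.002 | 0 | 1.014 | 1.007 | 5.2% | 5.6% |
| 0.02 | 0 | 1.14 | 1.068 | 6.6% | 7.3% |
| 0.02 | 0.01 | 1.06 | 1.030 | 5.7% | 5.7% |
| 0.02 | 0.02 | 0.98 | 0.990 | 4.8% | 4.4% |

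The last column is an unadjusted log-rank test simulated with 12 centres and 2 × 8 patients each, 6,000 runs per row. With no correlation the simulation gave 5.1%. Its Monte Carlo standard error is about √(0.05 × 0.95/6000) = 0.3 percentage points.

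**Effect of censoring deaths.** Let R be the true share responding and D the share dying before response. The total hazard is H = −ln(1 − R − D), of which R/(R + D) belongs to response. With deaths censored, 1 − KM = 1 − exp[−H × R/(R + D)]. For R = 0.50:

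| D (assumed) | H | 1 − KM | Overstatement (points) |
|---|---|---|---|
| 0.10 | 0.916 | 53.4% | 3.4 |
| 0.20 | 1.204 | 57.7% | 7.7 |
| 0.30 | 1.609 | 63.4% | 13.4 |
| 0.40 | 2.303 | 72.2% | 22.2 |

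If patients who die are instead kept at risk as non-responders to the end of follow-up, one minus Kaplan-Meier ends at R and the overstatement is zero, barring other censoring.

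**The case against.** The strongest reply is that these are details for a statistical analysis plan, which may exist but is not shown. A Cox model does not exclude stratification, a frailty or a robust variance, and censoring rules for secondary endpoints are often given there. This stands for the Cox model and for the handling of deaths, and it limits the severity. It does not fully cover the log-rank test. That is a named method, standard only for independent patients, set directly after a sentence that models clustering.

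Four stronger readings are tempting, and the protocol does not support them.

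- *Mortality p-values are wrong.* The listed mortality endpoint is assessed at day 28 and week 12. Those are percentages and fall under the hierarchical models, as does fever at day 7. Only a time-to-death analysis, if one is done, is affected.
- *Deaths are censored, so the response curve is biased.* The text does not say so. Item 6 refers back to a definition in which death is failure, so keeping those patients as non-responders fits the wording at least as well.
- *Overall 12-week mortality gives the size of the bias.* That figure includes deaths after a response, which do not compete with it. The upper rows of the second table are therefore not a prediction.
- *Response dates only reflect when unblinded physicians order scans.* Section 3 has a panel unaware of allocation review item 6. That protects classification. It does not standardise scan dates, so the grid of assessments remains an issue, but a bias by arm is not shown.

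The 6.6% is also one corner of the range: top correlation and nothing shared across periods. Section 4.4 calls the two coefficients equal. If that means equal correlation within and across periods, the unadjusted test is slightly conservative (4.8%).

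**Conclusion.** The point holds for the secondary time-to-event analyses only: time to global response, time to fever resolution, and time to death if analysed. As written, they do not carry the structure of the design. The consequence at the protocol's correlations is small: a correct standard error 0.99 to 1.07 times the unadjusted one and a true size of about 4.8% to 6.6% (simulated 4.4% to 7.3%), in either direction. The open question of deaths before response could matter more, with 3 to 22 points of overstatement for a true 50% response, but only if deaths are censored and only under the assumed 10% to 40% and constant hazards. Otherwise it is nil. The severity is minor to moderate. The primary analysis is not in question.

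**What to change.** In section 9, or in the analysis plan with a reference from section 9:

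1. For times to event, use a log-rank test stratified by centre, and a Cox model stratified by centre with a period term and either a cluster-period frailty or a cluster-robust variance. Add a small-sample correction, because there are only about 12 centres. Centre stratification removes stable centre differences but not cluster-period variation, so base inference on the Cox model.
2. Report response and fever resolution as cumulative incidence with death as a competing event, and say how deaths enter each analysis. Overall mortality has no competing event and can keep Kaplan-Meier.
3. Treat time to global response as interval-censored between assessments, or rely on the day-28 response percentage, for which the hierarchical model is already in place.

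The cost is analysis wording. No new data, visits or patients are needed.
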